# **1.0** INTRODUCTION

#### 1.1 Brief epidemiology of cutaneous melanoma

Of all cancers in the UK those of the skin are the commonest and comprise predominantly malignant melanoma, squamous cell carcinoma and basal cell carcinoma.

In the UK (2014), melanoma is the 5th most common cancer, accounting for 4% of all new cases of cancer (males: the 6th most common cancer, 4% of all male cases) (females: the 5th, 4% of all new cases).

Highlight figures: UK (2014): new cases of melanoma 15419, deaths 2459, (2% of all cancer deaths) with 10y survival (England&Wales) at 90%.

The projections for incidence rates of cutaneous melanoma are a rise by 7% in the UK between 2014 and 2035 to 32 cases per 100,000 people by 2035 with a larger increase for males than for females.

Skin cancer statistics | Cancer Research UK www.cancerresearchuk.org/health-professional/cancer-statistics/statistics.../ skin-cancer searched 2017nov

Worldwide, the incidence of invasive malignant melanoma is increasing faster than any other cancer (see references).

Excessive exposure to ultraviolet radiation in sunlight and especially when associated with sunburn is considered the prime predisposing factor which can be ameliorated by behavioural adaptation including the use of headwear, appropriate clothing and sunblock creams . Skin type or colour is also a crucial factor. Underlying genetic predisposition is also relevant where a first-degree relative has a history of malignant melanoma

(Skin Cancer prevention NICE Guidelines PH32 January 2011; Cancer Research UK Sunsmart; US National Cancer Institute-General Information about Melanoma).

### 1.2 Impact of clinical demands on the NHS

The large majority of pigmented moles are benign but concerns about the possibility of malignancy place a substantial load on health services. The proportion of patients who present in primary care concerned about moles who are referred on to dermatologists at secondary care centres with suspicion of malignancy is not well documented. Nonetheless a substantial proportion of those referred are considered by the

dermatologist to be benign by inspection without the need for mole removal and histology. When considered needed by the specialist patients are referred for excision biopsy and histology of the suspect lesion.

At Addenbrooke's Hospital the patients with pigmented cutaneous lesions which the specialist dermatologist/plastic surgeon on routine grounds considers require histopathology for diagnosis are normally sent for medical photography of the lesion(s) prior to the excision biopsy.

In Cambridge up to 1 in 10 of pigmented moles referred by specialist dermatologists for excision and histology are found to have melanoma (personal communication [name]).

There is thus room for using supporting methods or techniques to aid clinical decision making.

Management of potential melanoma lesions in England is guided by the Revised U.K. Guidelines for the management of melanoma 2010 British Association of Dermatologists, British Journal of Dermatology (2010) **163**, 238-256; NICE Guidelines: Skin Cancer (22/08/2017) https:// pathways.nice.org.uk/pathways/melanoma; and NICE Guidance: Melanoma assessment and management [NG14] (2015) http://bit.ly/2sdpnjW or https:// www.nice.org.uk/guidance/guidance/ng14

# **1.3** The nomela® test: using innovative technology to assist diagnosis

The innovative technology of the nomela® test aims to provide the clinician with a tool which, in suspicious pigmented skin lesions (moles), helps to exclude melanoma without biopsy, thereby providing a means of reducing referral rates for biopsy and histopathology.

1.3.1 Moletest Ltd. has developed a photographic image analysis system,

**nomela**®, using a modified iPad and proprietary software signal processing (the nomela® device). The software creates numerical values for several defined characteristics of the image some of which are not apparent to the naked eye.

(see section 4.3)

1.3.2 Early development of the technology accumulated information using library images of benign and malignant pigmented lesions against which thresholds were established to provide discrimination using a meta-engine.

(see Appendix A1)

1.3.3 In the Moletest clinical study 004 the definitive diagnosis of lesions referred from primary care to specialist dermatologists as suspicious of melanoma/malignancy was used to determine the ranges of 5 signal processing parameters obtained from the images which enabled separation into two groups, N "not-at-risk" containing no cases of melanoma and R "at-risk" containing all the cases of melanoma; both groups contained benign lesions.

(see Appendix A2)

#### 1.4 Summary of the clinical study C8

1.4.1 The nomela® technology is to be tested in this Study in secondary care by accumulating and analysing *in vivo* images of those pigmented skin lesions which are considered sufficiently suspicious to be referred by specialist dermatologist/plastic surgeon for biopsy/excision and histopathology. After a pilot phase of an initial 100 tests, the Study will involve testing 1200 to 2000 lesions such that completed tests on 200 melanoma have been accumulated.

1.4.2 The performance of nomela® will be assessed on all lesions tested by comparing the nomela® result (either "no evidence of melanoma" or "melanoma not excluded") with the subsequent confirmed diagnosis of "not-melanoma" or "melanoma" by histopathology.

(see Sections 4.2)

1.4.3 The ability to assign the lesions subjected to a nomela® test and subsequently confirmed as melanoma, to group R "melanoma not excluded" and by contrast not to group N "no evidence of melanoma" is to be evaluated.

Sensitivity and specificity of the nomela® test result for risk of melanoma will be determined. A high level of sensitivity is the objective.

(see 5.0) (see 1.4.3 and Appendix A2)

1.4.4 During the Study a participant's inclusion will not influence clinical management. There will be no change to routine care except for the short time required for the nomela® test.

#### 1.5 Parties to the Study and Agreements

For Agreements see separate documentation between the Parties:

- Moletest (Scotland) Ltd. SC478856
- Cambridge University Hospitals NHS Foundation Trust
- The University of Aberdeen

### 2.0 OBJECTIVES

1. To measure the performance of the **nomela**® test as a risk calculator for melanoma in pigmented skin lesions of patients referred by specialists for biopsy/excision and histopathology.

2. To demonstrate that the nomela  $\ensuremath{\mathbb{R}}$  test provides at least 95  $\pm$  2 % sensitivity for not-melanoma.

3. To complete a Usability Assessment (as per requirements of the relevant regulation covering medical devices EN62366).

4. Subsidiary objective: to construct a Health Economics Technology Assessment, details of which are developed separately.

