### 5.1 Sample size:

For this Study a total sample generating a minimum of 200 confirmed melanoma Cases will be evaluated. Of those lesions referred for histology by the Department of Dermatology it is estimated that from 1 in 6 up to 1 in 10 are found to be melanoma and thus approximately 1200 to 2000 lesions will be tested.

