5.2.2 Outcome measures

Primary outcome measure: sensitivity (95 % CI) of the nomela® test for not-melanoma.

Secondary outcome measure: the proportion (95% CI) of lesions that the nomela® test finds as having `no evidence of melanoma'.

5.2.3 The distribution of the nomela® test results between group N and R (see 1.4.3 & 3.6.2) for the Cases will be calculated. Estimates of sensitivity, specificity, positive and negative predictive values, and likelihood ratios (with 95% confidence intervals) will be calculated.

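### The ±2 in objective 2 is undefined: read as a 95% CI half-width it is not met by 200 melanomas (about ±3 points), and read as a 93% floor it demonstrates neither 95% nor 93%

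*Protocol*

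**What the plan says.** Section 2.0, objective 2, is to demonstrate that the "test provides at least 95" ± "2 % sensitivity for not-melanoma". No confidence level is attached, and the ±2 is not described as an interval width, a standard error or a tolerance.

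Section 5.2.2 names the primary outcome as "sensitivity (95 % CI) of the nomela® test for not-melanoma". The 95% interval is the only confidence level in the protocol, and no target width goes with it.

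Section 5.1 says that "a total sample generating a minimum of 200 confirmed melanoma Cases will be evaluated". The only calculation there converts 200 melanomas into lesions: "it is estimated that from 1 in 6 up to 1 in 10 are found to be melanoma", hence "approximately 1200 to 2000 lesions will be tested". The 200 itself is not derived from a precision, a margin or a power.

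Section 1.4.3 evaluates whether confirmed melanomas are assigned to group R, and adds: "Sensitivity and specificity of the nomela® test result for risk of melanoma will be determined". Section 3.8 ends the study for futility once 15 melanomas have received a result of no evidence of melanoma.

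**The concern.** The target joins a floor (at least 95%) to a plus-or-minus of 2 points, and the two do not make one criterion. A reader could take ±2 as the precision the study will deliver, as a margin that makes 93% acceptable, or as something else. The same data would then meet or miss the objective depending on the reading.

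This is the protocol's only numerical performance target. It sits on the primary outcome of a test meant to exclude melanoma without biopsy. For such a test the lower confidence limit carries the claim, because it bounds the share of melanomas that could be missed.

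**Working it through.** **Inputs.** Sensitivity 95% and ±2 points (2.0); two-sided 95% CI (5.2.2; two-sidedness is assumed); 200 melanomas as denominator (5.1, with 1.4.3 and 3.8); melanoma yield 1 in 6 to 1 in 10 (5.1).

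**The plan's own figure.** 200 × 6 = 1200 and 200 × 10 = 2000, so the lesion range reproduces exactly. The 200 has no stated derivation to reproduce.

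**Reading A: ±2 is the 95% CI half-width.**
- Half-width at n = 200: 1.96 × √(0.95 × 0.05 / 200) = 0.0302, or 3.0 points.
- Exact (Clopper-Pearson) 95% CI for 190/200: 91.0% to 97.6%.
- Melanomas needed for ±2: 1.96² × 0.0475 / 0.02² = 456.2, so 457. By the Wilson interval it is 465, by the exact interval 505. At 1 in 6 to 1 in 10, 457 melanomas mean 2742 to 4570 lesions.
- Melanomas needed for ±3: 1.96² × 0.0475 / 0.03² = 202.8, so 203, which is close to the planned 200.
- The most favourable pairing of the protocol's figures, 2000 lesions at 1 in 6, gives about 333 melanomas and a half-width of 2.3 points.
- At n = 200 the half-width falls to 2.0 points only when observed sensitivity is about 97.9% or more.

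**Reading B: ±2 is a tolerance, so the point estimate must be at least 93%.**
- 0.93 × 200 = 186, so up to 14 melanomas may be missed.
- This fits section 3.8: 14 missed is 186/200 = 93.0%, 15 missed is 185/200 = 92.5%.
- Exact 95% CI for 186/200: 88.5% to 96.1%.
- Probability of at least 186/200 (exact binomial): 0.92 if true sensitivity is 95%, 0.57 if it is 93%, 0.09 if it is 90%.

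**Reading C: the exact lower 95% limit must reach a threshold.**

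| Lower limit at least | Detected needed of 200 | True 95% | 96% | 97% | 98% | 99% |
|---|---|---|---|---|---|---|
| 93% | 194 (6 missed) | 0.12 | 0.31 | 0.61 | 0.89 | 0.996 |
| 95% | 197 (3 missed) | 0.009 | 0.04 | 0.15 | 0.43 | 0.86 |

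So 190/200, a point estimate of exactly 95%, passes under B and fails both rules in C.

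**Literal denominator.** If the denominator were the lesions that are not melanoma (1200 − 200 = 1000 to 2000 − 200 = 1800), the half-width at 95% would be 1.35 to 1.01 points, and ±2 would be met.

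**The case against.** The strongest reply is that the protocol never calls ±2 a 95% CI half-width and never claims that 200 melanomas deliver it. That stands: Reading A is conditional. Reading B is a live alternative, and the agreement between a 93% floor and the stop at 15 discordant melanomas is a real argument for it. But Reading B does not rescue the objective as worded. The aim is to demonstrate at least 95%, and 186/200 is compatible with a sensitivity below 89%. Section 3.8 is also framed as a futility stop, not as a criterion of success.

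Second, read literally, sensitivity for not-melanoma uses 1000 to 1800 lesions and ±2 is met. Sections 1.4.3, 3.8 and 5.1 all count melanomas, so this reading fits the design poorly. It does show that the wording of objective 2 and of the primary outcome needs correcting.

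Third, other meanings of ±2 are possible. One standard error would need 119 melanomas. An 80% interval would need 196, close to 200, but the protocol names no 80% level.

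Fourth, the decision rule may be in a statistical analysis plan that is not shown. Its absence from the protocol is therefore not held against the study. The ±2 and the 200 both stand in the protocol, however, and no later rule can make them agree at the 95% level for a sensitivity of 95%.

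Two stronger inferences are tempting and not supported. A reader might conclude that no success rule is attainable with 200 melanomas. That is wrong: a 93% point-estimate floor is met with probability 0.92 at a true 95%, and a lower limit of 93% with probability 0.89 at a true 98%. A reader might also count the 0.9% chance of a lower limit reaching 95% at a true 95% as a flaw of the sample size. It is not: a valid limit should rarely exclude the true value, whatever the number of melanomas.

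**Conclusion.** The point holds as an undefined target together with a conditional shortfall in precision. With melanomas as the denominator and a two-sided 95% interval, the minimum of 200 gives about ±3.0 points at 95% sensitivity, and ±2 would need about 457. Taken instead as a 93% point-estimate floor, the target can be met by data that demonstrate neither 95% nor 93%, and a test with true sensitivity 93% would meet it more often than not. A lower-limit rule at 93% is attainable but passes with reasonable probability only if true sensitivity is near 98%.

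The size depends on true sensitivity: the shortfall closes at about 97.9%. Melanomas beyond the minimum of 200 would narrow it. The arithmetic assumes independent lesions.

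**What to change.** Keep 200 melanomas and change the wording.

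1. In 2.0, and in the primary outcome in 5.2.2, state that sensitivity is for melanoma: confirmed melanomas assigned to group R, divided by all confirmed melanomas tested.
2. In 2.0 and 5.1, state that 200 melanomas estimate a sensitivity of 95% to within about ±3 points (exact 95% CI 91.0% to 97.6% for 190/200).
3. Replace the 95 ± 2% target with one rule on the exact lower 95% limit, at a threshold the sponsor chooses and justifies. Give the probability of meeting it at true sensitivities of 95% to 99%, as in the table above for 93% and 95%.
4. Reconcile that rule with section 3.8. With a 93% threshold and a final count of 200, for example, the rule is already lost at 7 missed melanomas while the study runs on until 15. Say whether that gap is intended.

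The change should be made before results are known. It costs protocol text and no extra participants; the price is a less favourable stated precision. If ±2 at the 95% level is really wanted, the cost is about 457 melanomas, or roughly 2740 to 4570 lesions.

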# 3.0 DESIGN

An open single-step non-randomised performance evaluation.

#### 3.1 Subject inclusion criteria

3.1.1 Patients referred on routine clinical decision by the Dermatology/ Plastic Surgery Departments for biopsy/excision and histopathology of suspicious pigmented skin lesions including as possible melanoma. 3.1.2 Patients aged 16 years and over.

Patients with a prior history of skin cancer will be included.

### 3.2 Subject (lesion) exclusion criteria

3.2.1 Other skin conditions not considered to be pigmented moles.

3.2.2 Lesions not considered suitable for nomela®. (see 3.3)

3.2.3 Patients unable or unwilling to give informed consent.

3.2.4 Patients aged less than 16 years.

#### 3.3 Prohibitions and restrictions

Lesions not considered suitable for nomela®:

pigmented moles smaller than 5mm diameter

moles obscured by hair or tattoos

moles in the mouth, eyelid, nailbed, genital and perianal areas

ulcerated lesions

non-pigmented moles which may be the amelanotic form of melanoma

lesions likely to be basal cell carcinoma, squamous cell carcinoma, Merkel cell tumours, lymphoma, metastatic carcinoma

[name]\2019apr05

# 3.4 Screening tests

No screening tests form any part of this study.

#### 3.5 Pilot phase

To provide reassurance that the nomela® software, defined after completion of study C7 and to be used by the nomela® device in C8, is performing technically as expected and reduce the risk of futile testing of up to 2000 participants, there will be an initial pilot phase of 100 tests.

If the observed rate of melanoma diagnosis in the pilot phase is found to be less than 1-in-12 (implying that more than 2400 lesions would need to be tested overall in the study at CUH to accumulate 200 melanoma) then the study would not continue at this site beyond the end of the pilot phase and alternative investigation sites would be sought.

#### 3.6 Study duration

The duration for recruitment of patients in the study is envisaged to be 6 months. Scrutiny of histopathology records will extend for no more than 12 weeks beyond the end of recruitment.

#### 3.7 Follow-up

No follow-up information is required for the study.

#### 3.8 Discordance limits

To avoid futile continuation of the Study where the nomela® test is demonstrably not performing as expected the Study shall be discontinued if the following condition is satisfied: when the nomela® tests for 15 melanoma are discordant ie where the nomela® result has been given as "No evidence of melanoma".

# 4.0 METHODS

# 4.1 The clinical visit

#### 4.1.1 Referral for clinical photography prior to excision biopsy

All patients referred on routine clinical decision by the Dermatology/ Plastic Surgery Departments for biopsy/excision and histopathology of suspicious pigmented skin lesions including as possible melanoma which satisfy the inclusion and exclusion criteria and suitability for nomela® testing will be invited to participate.

(see 3.1, 3.2, 3.3) The nomela® test is to be performed in clinic at the time of the standard photography. The Cambridge University Hospitals NHS Foundation Trust policy for use of a chaperone will be applied.

Operational aspects to minimise disruption to patient flow are considered.

#### 4.1.2 Consent to participation

Following provision of an accessible copy (paper or electronic) of the Patient Information Sheet to eligible patients, and with appropriate opportunity for oral explanation if required, Consent to participation will be sought in the Dermatology/Plastic Surgery clinic.

An e-consent format will be used (see v2.3e).

(see NHS HRA/MHRA Joint statement on seeking consent by electronic methods) https://www.hra.nhs.uk/documents/1588/hra-mhra-econsent-statement-sept-18.pdf (see Participant Information Sheet and Consent Form in separate documentation)

Withdrawal of consent: At the patient's request subsequent withdrawal of consent will be documented by a record of such withdrawal (date, mode of communication, name and signature of physician/nurse) attached to the original signed consent both of which are retained. The Clinical Research team must be advised of such withdrawal by email and will confirm removal from the Study by email to the Principal Investigator and the Sponsor. Following Withdrawal of Consent all information obtained during the nomela® test is deleted from the information stored and no use of the information is made.

#### 4.1.3 The nomela® test

The nomela® test will be performed by the trained operator (clinical research nurse) under the supervision of the Media Studio using the designated nomela® device provided for the Study by Moletest (Scotland) Ltd.

The time required for the test including identification, image acquisition and generation of test result should be 3 - 5 minutes (but less with experience).

(see 4.3 for technical aspects)

#### 4.1.4 Failure to complete a nomela® test

A list will be kept of pigmented moles sent for routine medical photography by the specialist in which the nomela® test was attempted but not completed with the reason for non-completion.

#### 4.1.5 Biopsy/excision and histopathology

The procedure for biopsy/excision and handling of tissue samples will follow the recognised practice at Cambridge University Hospitals NHS Hospitals Trust including written information and consent, preparation, documentation, sample identification and transfer to the Dept. of Pathology.

The Dept. of Pathology confirms following current national guidelines for reporting and of the retention/discard of tissue and prepared samples.

#### 4.2 Technical aspects of the nomela® test

#### 4.2.1 Equipment

Moletest (Scotland) Ltd. will provide the nomela® devices (modified Apple iPad) to the designated authorised personnel as follows:

Medical Illustration: to be used for supervising the nomela® test.

(see 4.2.2 - 4.2.7)

Clinical Research: to be used for the nomela® test and for access to the Study Log.

(see 4.2.5 and 4.3)

#### 4.2.2 Training of operators

Training in the use of the nomela® test is considered essential although the nomela® test is intuitive and brief. A short Training Programme is available for all prospective operators. Training will be provided by Moletest (Scotland) Ltd. and satisfactory completion of training will be recorded in a Training Log.

(see nomela® Screening Device Training Plan available separately)

#### 4.2.3 Conducting the nomela® test

The nomela® test follows a predetermined sequence. Authorised users log in. Date, time and place are recorded automatically. Patient identification is obtained by scanning, in this Study, of the hospital number.

The Participant number is generated automatically in this Study by the nomela® test. The string of the number allows for multiple lesions in one participant with a distinct digit for each lesion. In effect this is a combination participant-lesion number.

Location of the lesion is recorded in the nomela® test by regional and close-up images. This information may be used to correlate location information recorded by clinical correspondence and histopathology reports.

The close-up image is cropped manually by the operator to obtain optimal perimeter recognition and then accepted.

#### The nomela® test reference

A unique anonymised label, the nomela® reference, is generated randomly and automatically for each lesion during the nomela® test as a 128-bit number "universally unique identifier" (UUID) which is shown on the report page as a 2-dimensional QR code. This information will be inserted into the Study Log but is not required by the operators and clinical research team.

Tests on additional lesions which satisfy the Study criteria may be made in the same or different region each labelled by a separate nomela® test reference.

(and see section 4.3.5)

Unsuitable images: The nomela® test has been designed to reject any images of skin lesions that are unsuitable for analysis either because of an uncertain border or because they are too small (less than 7000 data points per image). The number of such lesions which do not satisfy these capture criteria will be recorded.

Standardisation of lighting: Images are captured using available light. Any lighting should be diffuse and the source (window or ceiling lights) should be at least 2 metres away to avoid any flare on or around the lesion. Positioning of device and lesion: The nomela® device should be

positioned to obtain a sharp focussed close-up image, on a plane parallel with the lesion, with neither a requirement for varied angles nor cross lighting.

(see separate document: Instruction for nomela® test image capture)

